## 12. Appendix A: Schedule of Events

Study Event	Screening Visit	Visit 1	Visit 2	Visit 3	Visit 4	Visit 5 to Visit 9	Early Termination
	Screening a (-30 days)	Day 1 a	Day 8 (+3 days)	Day 15 – Phone (+3 days)	Month 1 (±3 days)	Months 2, 3, 4, 5, 6 – Phone (±5 days)	
Informed Consent	X						Refer to Section 7.2 for Procedures
Demographics, Medical History	X	X b					
Concomitant Medications	X	X	X	X	X d	X d	
Physical Exam(s), targeted	X	X b					
Vital Signs	X	X c					
Confirmation of Eligibility	X	X					
Randomization		X					
Study Vaccine Administration		X					
Post-vaccination Observation (at least 30 minutes)		X					
Issue eDiary instructions, Ruler, Thermometer; Conduct Training/Retraining		X					
Review eDiary Data			X				
AE Evaluation (Solicited and/or Unsolicited)		X	X	X	X	X d	
Clinical Labs							
Hematology, Chemistry, Urinalysis		X b			X		
Urine Pregnancy	X b	X b					
Serum for Immunogenicity		X b			X		

- a) Screening and Day 1 Visit are encouraged to be combined; however, subjects may screen for up to 30 days prior to randomizing into the study, and a separate Screening visit may be conducted.
- b) Conduct or collect prior to study vaccination (if indicated by updated medical history or change in health status, as applicable).
- c) Vitals to be taken before and  $\geq 30$  minutes after study vaccine administration.
- d) Only NOCI, MAAE, SAE, and associated concomitant medications collected after Month 1.

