For each unsolicited AE collected for a subject, the maximum relationship will be the strongest relationship, as per Investigator, for all occurrences of this AE. There will be no replacement in case of missing relationship.

- **Time of first onset of first event (days):**

Day of onset of the first solicited AE, as per the nominal visit where the first solicited AE was first reported. This will range from 1 (Day 1 = Day of study vaccine administration) to 7 (Day 7).

- **Duration of solicited AEs (days):**

Number of days between the onset of the solicited AE (i.e. nominal visit of first occurrence of Grade \geq 1) and the end of the solicited AE (i.e. nominal visit when Grade is back to 0). If there are different occurrences of a same solicited AE within 7 days, the durations will be added up. For solicited AEs continuing beyond 7 days, the end day of the continuing unsolicited adverse event will be used as the end day for the calculation. If the unsolicited AE is ongoing (i.e. stop date is missing), then duration will be the Number of days between the onset of the solicited AE and the study discontinuation date.

Example 1: If a subject has a solicited event Pain starting on Day 1 and finishing on Day 4, the duration is 4.

Example 2: If a subject has a solicited event Fatigue starting on Day 2 and finishing on Day 3. And a new solicited event Fatigue starting on Day 7 and ending on Day 9. The Duration will be 2+3=5.

Frequencies and percentages of subjects experiencing each solicited AE will be presented overall and by severity. For each of the time points or time intervals presented in the summaries, only subjects with at least one observation (ie, any non-missing values but excluding "Not done/unknown") for the solicited AEs will be summarized.

The following summaries of subjects will be performed:

- Solicited AEs within 7 days post-injection, for each event and for any event, overall and by maximum severity. Details by category (local, systemic) will also be presented. (Severity as per Investigator)
- Possibly or probably related solicited AEs within 7 days post-injection, for each event and for any event, by maximum severity (Severity and Relatedness as per Investigator) This summary will only be presented on the Overall (50+) population.

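### The SAP's solicited-AE duration rule does not give one count that fits its own examples, and it enters prolonged events with no stop date as completed durations of about 180 days

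*SAP*

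**What the plan says.** SAP 6.5.1.1 defines the duration of a solicited AE as the days between its onset, the nominal diary day of the first grade of 1 or more, and its end. Separate episodes of the same event are added together. Three different ends are used:

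- For an episode that ends within the diary, the end is the "nominal visit when Grade is back to 0".
- For an event that continues beyond 7 days, "the end day of the continuing unsolicited adverse event will be used as the end day for the calculation".
- If that continuing event has no stop date, "then duration will be the Number of days between the onset of the solicited AE and the study discontinuation date".

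Two examples follow. The first reads: "If a subject has a solicited event Pain starting on Day 1 and finishing on Day 4, the duration is 4". The second counts Day 2 to Day 3 as 2 days and Day 7 to Day 9 as 3 days, 5 in total.

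SAP 6.2.6 leaves missing AE stop dates unimputed and treats those events as ongoing. SAP 6.2.1 reports mean, median, standard deviation, minimum and maximum for continuous variables. SAP 6.5 repeats the safety summaries by treatment group, overall and for ages 50-59, 60+ and 65+. Protocol 10.6.2 plans summaries of the duration of each solicited event and of the maximum duration of any event. On collection after Month 1, footnote d of the protocol's Schedule of Events says: "Only NOCI, MAAE, SAE, and associated concomitant medications collected after Month 1".

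**The concern.** There are two separate weaknesses.

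The first is the counting rule. Diary episodes and prolonged episodes end on different kinds of day: the first symptom-free day for one, the recorded AE end day for the other. The SAP does not say whether the first and last days both count, or whether the finishing day in the examples is the last day with symptoms or the first day without. It writes the extra day out explicitly elsewhere, for time on study (5.2) and for AE onset (6.5.1.2), but not here. Two programmers could differ by one day per episode, which is the whole length of a one-day reaction. The diary data analysed run from Day 1 to Day 7, so an episode still present on Day 7 and gone by Day 8 never shows a Grade 0 day and is not prolonged either.

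The second is the rule for prolonged events with no stop date. The time to study discontinuation is a follow-up time, but it enters the mean and maximum as though resolution had been observed on that date. A non-serious reaction that settled after Month 1 could easily lack a stop date, because the Month 2 to 6 calls evaluate only SAE, NOCI and MAAE. A single record could then look like a tolerability difference between dose groups.

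**Working it through.** **Counting rule.** Apply each reading to the three example episodes. For diary episodes the rule's end is the Grade 0 day. If the finishing day means the last symptomatic day, Grade 0 falls one day later. For the Day 7 to 9 episode the end is the AE end day, taken as Day 9 because the example has it ending then.

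| Finishing day means | Count | Day 1-4 (stated 4) | Day 2-3 (stated 2) | Day 7-9 (stated 3) |
|---|---|---|---|---|
| Grade 0 day | end − start | 4−1 = 3 | 3−2 = 1 | 9−7 = 2 |
| Last symptomatic day | end − start | 5−1 = 4 | 4−2 = 2 | 9−7 = 2 |
| Grade 0 day | end − start + 1 | 4−1+1 = 4 | 3−2+1 = 2 | 9−7+1 = 3 |
| Last symptomatic day | end − start + 1 | 5−1+1 = 5 | 4−2+1 = 3 | 9−7+1 = 3 |

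Only the third row reproduces every figure, and it counts a symptom-free day in each diary episode: a reaction present on Day 1 only, with Grade 0 on Day 2, gets 2−1+1 = 2 days. The second row could be rescued if sites recorded the AE end day as the first symptom-free day (10−7 = 3), but the SAP does not say so.

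A single convention removes the problem. With last symptomatic day − first symptomatic day + 1, the examples give 4−1+1 = 4, and (3−2+1) + (9−7+1) = 2+3 = 5. A reaction present on Day 7 only gives 7−7+1 = 1.

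**Events with no stop date.** Inputs: Month 6 is 180 days after Day 1, ±5 days (protocol 4.3, 7.1.6), so study Day 176 to 186; onset is Day 1 to Day 7. The SAP does not say what the discontinuation date is for a completer, so I take the Month 6 contact.

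- Shortest, by subtraction: 176−7 = 169 days.
- Longest, counted inclusively: 186−1+1 = 186 days.
- Nominal: 181−1 = 180 days.

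**Shift in an arm's mean from one such record.** Inputs: 250 per arm (protocol 10.3); approximate PCV20 reaction rates from the VAX-24 studies (protocol 2.1), applied to any arm; and a typical duration m of 2 to 3 days, which is my assumption. The shift is (180 − m)/n, where n is the number of subjects with the reaction.

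| Event | Rate | n | Shift, m = 2 | Shift, m = 3 |
|---|---|---|---|---|
| Pain | 70% | 175 | 178/175 = 1.02 | 177/175 = 1.01 |
| Muscle pain | 50% | 125 | 1.42 | 1.42 |
| Fatigue | 40% | 100 | 1.78 | 1.77 |
| Headache | 30% | 75 | 2.37 | 2.36 |
| Joint pain | 20% | 50 | 178/50 = 3.56 | 177/50 = 3.54 |

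For 65+, the minimum of 200 subjects over four arms gives about 200/4 = 50 per arm. Pain then has n = 35 and a shift of about 5.1 days; joint pain has n = 10 and a shift of about 17.7 to 17.8 days. In every case the arm's maximum becomes roughly 180 days.

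**The case against.** A reader might infer that the rule flatly contradicts its examples by one day in every episode. The documents do not support that. Read finishing as the last day with the symptom, and subtraction to the Grade 0 day fits both diary examples; all three example figures plausibly count symptomatic days. What stands is that this reading does not carry over to the Day 7 to 9 episode as the rule is written.

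A reader might also infer that any reaction without a stop date is given about 180 days. It is not. The rule reaches only events that continued past Day 7, were entered on the unsolicited AE page as prolonged, and have no stop date there.

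The strongest defence concerns frequency. Stop date is an expected item for every AE (protocol 8.5.2). AEs are reviewed at Day 8, Day 15 and Month 1, and unscheduled visits are allowed. Investigators must follow all AEs to resolution, stabilization or loss of clinical significance, or until nothing more can be learned (protocol 8.4). The SAP expects diary and AE pages to be reconciled before the interim lock, and protocol 2.1 describes these reactions in the VAX-24 studies as typically self-limiting. The number of open records could be zero. All of this stands, with one qualification: protocol 8.4 itself lets follow-up end without resolution, so an event can properly have no stop date.

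It is also fair that the median is planned, that prolonged events have their own summary and listing (SAP 6.5.1.3), so an outlier would be traceable, and that for an event truly ongoing the elapsed time understates its length. That last point confirms that the value is a censoring time. It does not justify averaging it with observed durations.

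**Conclusion.** The point holds as a needed clarification of a descriptive tolerability summary. The counting rule does not settle one convention consistent with its examples, at a cost of up to one day per episode, and it leaves an episode present on Day 7 but not prolonged without an end. The rule for prolonged events with no stop date puts about 169 to 186 days into the mean and maximum as if observed. One such record in a completer shifts an arm's mean by about 1.0 day (pain) to 3.5 days (joint pain), or about 5 to 18 days at roughly 50 per arm in 65+.

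These sizes assume the protocol's approximate PCV20 reaction rates, a typical duration of 2 to 3 days, and follow-up to Month 6; a subject who leaves early gets a shorter value. It would go too far to say that reported durations will be wrong, because the documents give no frequency for such records. The median moves little. Duration is neither a primary nor a secondary endpoint, so the primary percentages of subjects with reactions are unaffected.

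A related gap: at the Month 1 interim lock, subjects still in the study have no discontinuation date, so the rule gives no value for their open events if duration is part of that delivery.

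**What to change.** In SAP 6.5.1.1:

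- (a) Define the end of an episode as the last day with a grade of 1 or more, or the AE stop date if the event is prolonged. Define duration as end minus start plus 1, summed over episodes. This reproduces both examples and covers an episode present on Day 7.
- (b) Do not enter events without a stop date into the mean and maximum as completed durations. Report their number as ongoing, by arm, and list the time to the last AE assessment. Summarise completed durations separately, and apply the same rule to the maximum duration of any event. If a median over all events is wanted, name a censored-data method such as Kaplan-Meier, and say how a subject with one open episode among several is handled.

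The cost is a short SAP revision, an extra row in the duration tables and minor programming; a Kaplan-Meier summary would add somewhat more. The downside is that unresolved events appear as a count instead of a long duration, so the mean of completed durations must be read together with that count.

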6.5.1.2. Unsolicited Adverse Events

An unsolicited AE is an AE that is spontaneously reported by the subject or discovered by the Investigator. SAEs, NOCIs and MAAEs would be recorded as part of the collection of unsolicited AEs as specified in the visit procedures. Unsolicited AEs are collected separately from solicited AEs.

Solicited AEs continuing beyond 7 days will be identified using rules given in Section 5.2. They will not be presented in the summaries of unsolicited Adverse Events, but only in a Listing.

The definition of a treatment emergent AE (TEAE) is an event that occurs after vaccination and within the 30 days after vaccination (i.e., excluding those after a subject has given informed consent, but before vaccination):

- Onset (days) = Start date of AE – Date of Study Vaccine Administration + 1
- An AE is a TEAE if Onset \geq 1 and Onset \leq 30 and is not a continuing solicited AE

Adverse events are summarized by subject, therefore, in any tabulation, a subject contributes only once to the count for a given adverse event (SOC or preferred term).

Unsolicited AEs will be coded using the Medical Dictionary for Regulatory Activities (MedDRA) and will be summarized by decreasing frequency of SOC and preferred term within SOC in the control group, as follows:

- Unsolicited TEAEs
- Possibly or probably related unsolicited TEAEs
- Unsolicited TEAEs leading to study withdrawal

- SAEs
- Possibly or probably related SAEs
- NOCIs
- Possibly or probably related NOCIs
- MAAEs
- Possibly or probably related MAAEs
- AEs leading to death (only presented on the Safety Population overall)

Following summaries will be presented on the Safety Population overall only by decreasing frequency of PT, with an additional column “VAX-31” combining all subjects vaccinated with any dose of VAX-31:

- Unsolicited TEAEs
- Possibly or probably related unsolicited TEAEs

Following by-subject Listings will be provided:

- Pre-vaccination AEs (non-emergent)
- All unsolicited TEAEs
- All Serious post-vaccination AEs, NOCIs and MAAEs

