### **6.11   Solicited Adverse Events**

Solicited AE will be collected for 7 days after vaccine administration, starting on Day 1. Solicited AE for this study are local events of pain, erythema (redness) and edema (swelling) at the injection site, and systemic events of oral temperature  $\geq 100.4^{\circ}\text{F}$ , fatigue, headache, muscle pain, and joint pain.

Subjects will be trained to complete an electronic diary (eDiary) via Zelta's electronic Patient Reported Outcomes (ePRO) system. The eDiary collects the primary safety endpoint data. This system is accessed via a secure URL and will be used to observe, measure, and record these solicited AE. A digital thermometer will be provided to the subject to measure oral temperature each day, and it is to be recorded daily in the diary. To record injection site local reaction, a ruler will be provided to the subject to measure the diameter of redness and swelling at the largest point of the reaction each day; it is to be recorded daily in the diary. Study staff will be provided with a Reference Guide for instructing subjects on accessing the Zelta ePRO system. Each user will be provided with login credentials and a temporary password. The Zelta ePRO system is web-based and accessed via a secure URL.

Study staff will review the signs and symptoms recorded in the diary and the action taken for the event during the subject's clinic visit. The electronic diary will serve as the primary source document and data will be automatically integrated into the subject visit Solicited AE form in the EDC platform for site staff view-only access. The Investigator will then assess all recorded solicited events for severity and relatedness. Severity will be graded according to the FDA Toxicity Grading Scale ([FDA, 2007](#)). The results of the Investigator's assessment, if different from the subject's entry, will be recorded in a separate eCRF specified for Investigators. For solicited injection site reactions, the relationship to study vaccine will be automatically recorded to be probably related, however, the Investigator will determine the relationship for each systemic solicited reaction.

Symptoms continuing beyond the solicited AE collection period (7 days following injection) will be collected and recorded as unsolicited AE in the source document. The start date of unsolicited AE will be equal to the date of onset of the solicited AE.

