# 8. Safety

## 8.1 Definitions

### 8.1.1 Adverse Event

An AE is any untoward medical occurrence in a study subject, regardless of the suspected causal relationship with study vaccine. The definition of an AE includes:

- A new-onset symptom or disease
- An exacerbation of a pre-existing symptom or disease
- A new-onset clinical laboratory abnormality considered by the Investigator to be clinically significant
- A new-onset symptom or disease that occurs as a result of a protocol-specified procedure

The definition of an AE does **not** include:

- A pre-existing symptom or disease that does not worsen during the study (even if first disclosed by the subject after the start of the study)

- A medical or surgical intervention such as surgery, endoscopy, tooth extraction, or transfusion (although the condition leading to the procedure or a complication from the procedure may be an AE)
- An uncomplicated pregnancy
- A dosing error without any resulting signs or symptoms
- Any other situation where an untoward medical occurrence has not occurred (e.g., hospitalization for cosmetic elective surgery or social admissions)

The definition of a treatment emergent adverse event (TEAE) is an event that occurs after vaccination and within 30 days after vaccination (i.e., excluding those after a subject has given informed consent, but before vaccination).

The definition of a medically attended adverse event (MAAE) includes:

- A new onset or worsening of a condition that prompts the subject to seek unplanned medical advice at a physician's office, urgent care center, or Emergency Department

The definition of a new onset of chronic illness (NOCI) includes:

- A new onset of a disease or condition that requires ongoing medical attention and/or limits activity of daily living, e.g., heart disease, cancer, diabetes

The Investigator will attempt to establish a diagnosis based on signs, symptoms, and other clinical information. Whenever possible, the Investigator will report an AE as a diagnosis rather than 1 or more signs or symptoms. If a clinically significant laboratory abnormality meets the definition of an AE, a diagnosis or clinical signs and symptoms rather than the abnormal clinical laboratory finding should be reported if possible. If no diagnosis is known and clinical signs and symptoms are not present, but the laboratory abnormality is clinically significant by itself, then it should be reported as the AE.

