### **8.1.3 Unsolicited Adverse Event**

An unsolicited AE is an AE that is spontaneously reported by the subject or discovered by the Investigator. New onset of chronic illness(es) would be recorded as part of the collection of unsolicited AE as specified in the visit procedures. Unsolicited AE will be collected separately from solicited AE. Solicited AE occurring or persisting beyond the solicitation period or which meet SAE/NOCI/MAAE criteria are also recorded as unsolicited AE.

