### **10.6.3 Unsolicited Adverse Events**

All the unsolicited AE occurring during the study will be recorded, regardless of their assessment of relatedness by the Investigator.

The original verbatim terms used by Investigators to identify AE will be mapped to preferred terms using the MedDRA dictionary. The unsolicited AE will then be grouped by MedDRA preferred terms into frequency tables according to system organ class (SOC). All reported AE, as well as AE judged by the Investigator as at least possibly related to study vaccine, will be summarized by treatment group, according to SOC and preferred term within SOC. When an unsolicited AE occurs more than once for a subject, the maximum severity reported and strongest reported relationship to the treatment group will be counted.

Only TEAE will be summarized as defined in Section 8.1.1. The selection of unsolicited AE and their assignment to time intervals will be done by day of onset and not by days ongoing/persisting.

Unsolicited AE will be summarized by alphabetic SOC and preferred term as follows:

- Any unsolicited TEAE
- Possibly or probably related unsolicited TEAE
- SAE
- Possibly or probably related SAE
- NOCI
- MAAE
- Unsolicited TEAE leading to withdrawal
- Any AE leading to death

Listings of all TEAE will be provided by subject.

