### **10.6.4 Combined Solicited and Unsolicited Adverse Events**

Solicited AE continuing beyond 7 days after an injection will be coded by MedDRA and combined with the unsolicited AE. An overall summary of subjects with all combined solicited and unsolicited AE, by SOC and preferred term, will be provided as well.

[REDACTED] [REDACTED] [REDACTED]

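### SAP 6.5.1.2 leaves open whether serious or medically attended reactions that cross Day 7 count in the primary SAE, NOCI and MAAE percentages, and its TEAE rule empties a table in 6.5.1.3

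*SAP*

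**What the plan says.** **Protocol.** The percentages of subjects with an SAE, NOCI or MAAE within 6 months are primary endpoints (Protocol 3.1, repeated in SAP 3.2), with no exclusion by type of event. Protocol 8.1.4 allows an SAE to be a solicited or an unsolicited event. Protocol 8.1.3 adds: "Solicited AE occurring or persisting beyond the solicitation period or which meet SAE/NOCI/MAAE criteria are also recorded as unsolicited AE". Protocol 6.11 fixes the date of the carried-over record: "The start date of unsolicited AE will be equal to the date of onset of the solicited AE". Protocol 8.1.1 defines treatment emergence by timing alone: "The definition of a treatment emergent adverse event (TEAE) is an event that occurs after vaccination and within 30 days after vaccination". Protocol 10.6.3 adopts that definition: "Only TEAE will be summarized as defined in Section 8.1.1". Protocol 10.6.4 then says: "Solicited AE continuing beyond 7 days after an injection will be coded by MedDRA and combined with the unsolicited AE".

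**SAP.** Section 5.2 identifies prolonged solicited reactions by one yes/no question on the unsolicited AE page. Section 6.5.1.2 says of them: "They will not be presented in the summaries of unsolicited Adverse Events, but only in a Listing". It codes a TEAE as an event with onset on Day 1 to Day 30 "and is not a continuing solicited AE". The same section places SAEs, NOCIs and MAAEs within the unsolicited AE collection. It names their tables, and the death table, in the list of summaries of unsolicited AEs. It also asks for a listing of "All Serious post-vaccination AEs, NOCIs and MAAEs", without restriction. Section 6.5.1.3 asks for a summary of solicited TEAEs that last past 7 days, a summary combining them with unsolicited TEAEs, and a listing. Section 7 declares no difference from the protocol's analyses.

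**The concern.** There are three linked problems.

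1. **Scope of three primary endpoints.** The sentence that removes prolonged reactions from the unsolicited AE summaries comes before a list that contains the SAE, NOCI, MAAE and death tables. One programmer could drop flagged records from all of them, and another could keep them. The results would be different primary percentages from the same data. On the literal reading, the listing of serious, NOCI and MAAE events would show events that the tables do not count.
2. **An undeclared change to the TEAE definition.** The SAP adds an exclusion that the protocol does not have, and Section 7 says nothing has changed.
3. **Internal conflict.** The added clause removes exactly the events that 6.5.1.3 sets out to tabulate. Restricting them to a listing also contradicts 6.5.1.3, which summarizes them.

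Safety is reported descriptively, so the percentages are themselves the primary result. No later test or model would expose a difference in counting rules.

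Some things are not in dispute. A prolonged reaction still counts in the 7-day solicited endpoints and is listed. Section 6.5.1.3 is plainly meant to tabulate it. Showing it apart from the unsolicited TEAE table is defensible under Protocol 10.6.4.

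**Working it through.** The plan gives no figure on this point to reproduce. The check is one of set logic, followed by simple arithmetic for scale.

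**Step 1: the two readings of the SAE, NOCI and MAAE tables.**
- *Excluded:* SAP 6.5.1.2 bars prolonged reactions from the unsolicited summaries, these tables are in that list, and the 5.2 flag takes no account of seriousness or medical attendance.
- *Included:* the coded exclusion is attached only to the TEAE definition, these table titles do not carry the TEAE label, SAP 3.2 has no carve-out, and Protocol 8.1.3 and 8.1.4 count such events.

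The dividing line is crossing Day 7, not length. In SAP 6.5.1.1, Example 2, fatigue on Days 7 to 9 lasts 3 days and is prolonged. A reaction on Days 1 to 7 lasts 7 days and is not.

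**Step 2: the TEAE definition.** Under Protocol 6.11 a prolonged record starts on the onset day of the solicited reaction, which is Day 1 to Day 7. That is within 30 days, so every prolonged reaction is a TEAE under the protocol. Under the SAP none is.

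**Step 3: five illustrative records.**

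| Record | Onset day | Prolonged solicited | Medically attended |
|---|---|---|---|
| 1 | 2 | yes | yes |
| 2 | 3 | yes | no |
| 3 | 10 | no | yes |
| 4 | 12 | no | no |
| 5 | 60 | no | yes |

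- Protocol TEAEs: records 1 to 4, so 4.
- SAP TEAEs: records 3 and 4, so 2.
- Prolonged solicited TEAEs under the SAP: prolonged AND (onset Day 1–30 AND not prolonged) = 0. This holds for any data.
- Combined 6.5.1.3 summary: records 3 and 4, identical to the unsolicited TEAE table.
- Attended events: 2 (records 3 and 5) on the literal reading, 3 (records 1, 3 and 5) on the inclusive one.

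**Step 4: size per omitted subject**, for a subject with no other qualifying event, as 100/n. The arm size of 250 is from Protocol 10.3. The age-group sizes divide the planned numbers equally among four arms, which is an assumption.
- All subjects: 100/250 = 0.4 points.
- 50–59 (up to 600, so 150 per arm): 100/150 = 0.67 points.
- 60 and older (about 400, so 100 per arm): 100/100 = 1.0 point.
- 65 and older (minimum 200, so 50 per arm): 100/50 = 2.0 points.

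**Step 5: relative size**, assuming VAX-31 has the VAX-24 rates quoted in Protocol 2.1.
- MAAE: 0.113 × 250 = 28.25 subjects per arm. One subject is 1/28.25 = 3.5% of the count.
- NOCI: 0.019 × 250 = 4.75. One subject is 1/4.75 = 21%.
- SAE: 0.012 × 250 = 3.0. One subject is 1/3 = 33%.

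**Step 6: frequency, by assumption only.** Suppose 1–5% of subjects have a prolonged reaction and 5–20% of those are medically attended. Neither range has a source in the documents.
- Affected share: 0.01 × 0.05 = 0.05% to 0.05 × 0.20 = 1.0%.
- Per arm: 0.0005 × 250 = 0.125 to 0.01 × 250 = 2.5 subjects.
- At least one among 1000: 1 − 0.9995^1000 = 0.39 to 1 − 0.99^1000 > 0.99.

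**The case against.** The strongest reply is that the inclusive reading is the better one. The primary endpoints have no carve-out, the protocol says a solicited event can be an SAE, and the coded exclusion belongs to TEAEs only. Lead-in sentences are also a poor guide to scope here. Protocol 10.6.3 limits its summaries to TEAEs and then lists SAE, NOCI and MAAE tables, yet nobody would cut those 6-month endpoints to 30 days. This makes the inclusive reading more likely to be intended. It does not make it stated, and the SAP's lead-in does cover those tables.

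On 6.5.1.3, SAP 6.5.1.1 sends prolonged reactions there to be combined and described, and 6.5.1.3 selects them by the 5.2 flag. A sensible programmer would probably fill the table from the flag. The intent is clear, but following it means ignoring the SAP's own TEAE rule. The combined summary would not be empty, only redundant.

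On size, the frequency inputs in Step 6 are unsourced, and the probabilities only restate them. They concern medical attendance and say nothing about how often a prolonged reaction is serious. Protocol 2.1 describes VAX-24 solicited events as typically mild to moderate and self-limiting, and reports no related SAE or NOCI. Realistic exposure is therefore mainly in MAAE. There the assumed shift of 0.05 to 1.0 points is small beside the sampling error: 1.96 × √(0.113 × 0.887/250) = 3.9 points. All of that stands. It limits the likely effect and leaves the ambiguity in place.

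**Conclusion.** The concern holds. Followed literally, SAP 6.5.1.2 drops qualifying events from the primary SAE, NOCI and MAAE percentages. An equally documented reading keeps them, and no text decides between the two. The TEAE definition departs from Protocol 8.1.1 without declaration. As a matter of logic and for any data, it empties the first 6.5.1.3 summary and the matching listing, and makes the combined summary a duplicate.

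The effect is 0.4 points per omitted subject in a full arm and about 2.0 points in the 65-and-older group, given equal allocation within age groups. How many subjects would be affected, and whether that differs by dose, cannot be known from the documents. MAAE is the most exposed endpoint. An omitted SAE would be rarer but would weigh more, at about one third of the expected count if VAX-24 rates applied.

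**What to change.** In SAP 6.5.1.2:

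- State that the SAE, NOCI and MAAE summaries, their related-event versions and the death summary include every qualifying post-vaccination AE, whatever the answer to the prolonged-solicited question.
- Remove the added exclusion from the TEAE definition so that it matches Protocol 8.1.1. If prolonged reactions are to stay out of the unsolicited TEAE tables, apply that as a named filter on those tables only, with 6.5.1.3 giving the prolonged and combined views.
- Replace the restriction to a listing with a reference to 6.5.1.3.

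In SAP Section 7, declare any departure from the protocol that remains.

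The cost is a few sentences and one filter change in the AE programs. If the literal reading would otherwise have been programmed, reported SAE, NOCI and MAAE percentages may rise slightly. Sample size, data collection and visits do not change.
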